## L COMMON RISK FACTORS FOR ARDS

### Direct

Pneumonia

Aspiration of gastric contents

Inhalational injury

Pulmonary contusion

Drowning

### Indirect

Non-pulmonary sepsis

Major trauma

Pancreatitis

Severe burns

Non-cardiogenic shock

Drug overdose

Multiple transfusions or transfusion associated acute lung injury (TRALI)

Source: Supplementary Online Content, eTable 1. The ARDS Definition Task Force. Acute respiratory distress syndrome: the Berlin Definition. JAMA. doi:10.1001/jama.2012.5669.

## L ICU MOBILITY SCALE [20]

	Classification	Definition
0	Nothing (lying in bed)	Passively rolled or passively exercised by staff, but not actively moving
1	Sitting in bed, exercising in bed	Any activity in bed including rolling, bridging, active exercises, cycle ergometry and active assisted exercises; not moving out of bed or over edge of bed
2	Passively moving to chair (no standing)	Hoist, passive lift or slide transfer, to the chair, with no standing or sitting on the edge of the bed
3	Sitting over edge of bed	May be assisted by staff, but involves actively sitting over the edge of the bed with some trunk control
4	Standing	Weight bearing through the feet in the standing position, with or without assistance. This may include use of a standing lifter device or tilt table.
5	Transferring bed to chair	Able to step or shuffle through standing to the chair. This involves actively transferring the weight from one leg to the other to move to the chair. If the patient has been stood with the assistance of a medical device, they must step to the chair (not included if the patient is wheeled in a standing lifter device).
6	Marching on spot (at bedside)	Able to walk on the spot by lifting alternate feet (must be able to step at least 4 times, twice on each foot), with or without assistance.
7	Walking with assistance of 2 or more people	Walking away from bed/chair by at least 5 m (5 yards) assisted by 2 or more people
8	Walking with assistance of 1 person	Walking away from bed/chair by at least 5 m (5 yards) assisted by 1 person
9	Walking independently with a gait aid	Walking away from bed/chair by at least 5 m (5 yards) with a gait aid but no assistance from another person. In a wheelchair bound person, this activity involves wheeling the chair 5m (5 yards) away from the bed/chair.
10	Walking independently without a gait aid	Walking away from bed/chair by at least 5 m (5 yards) without a gait aid, or assistance from another person.

# Introduction

The following document is the Statistical Analysis Plan for the ROSE Study. It describes the study and the statistical methods used to analyze the primary and secondary outcomes in the study. Appendix A is a list of all variables that will be analyzed in the study along with their classification, and analysis method. Appendix B is the definition of all derived and composite variables, and the data imputation rules for all variables where imputation is used.

## 1. Trial Summary

### 1.1 Background

In 2010, the ACURASYS trial reported early neuromuscular blockade (also called skeletal muscle relaxant or muscle relaxant) administration improved adjusted survival for moderate to severe ARDS in a 340 patient trial conducted in 20 French ICUs. While intriguing, this approach has not been widely adopted in the U.S., and key limitations exist. First, the trial was underpowered. Mortality benefit was noted only after statistical adjustment; crude 90d mortality did not differ. Control mortality was also lower than predicted (though higher than many recent ARDS trials) and the authors concluded “given the observed mortality in our placebo group, the current study was underpowered”. Second, the mechanism responsible for the improvement in outcome with neuromuscular blockade is unclear. One possible explanation is that neuromuscular blockade results in improvement in patient-ventilator asynchrony with subsequent reduction in ventilator-induced lung injury and inflammation. Third, assessment of a known side effect of the intervention, muscle paresis, has been criticized as inadequate. As a result of these concerns, the critical care community has collectively recommended another phase III clinical trial to definitively test the safety and efficacy of neuromuscular blockade in patients with ARDS.

### 1.2 Inclusion Criteria

1. Age  $\geq$  18 years
2. Presence of all of the following conditions for  $\leq$  48 hours
  - i. (I)  $\text{PaO}_2/\text{FiO}_2 < 150$  with  $\text{PEEP} \geq 8 \text{ cm H}_2\text{O}$ .a,b,c

#### **OR, IF ABG NOT AVAILABLE**

$\text{SpO}_2/\text{FiO}_2$  ratio that is equivalent to a  $\text{PaO}_2/\text{FiO}_2 < 150$  with  $\text{PEEP} \geq 8 \text{ cm H}_2\text{O}$  (Appendix A1), and a confirmatory  $\text{SpO}_2/\text{FiO}_2$  ratio between 1-6 hours after the initial  $\text{SpO}_2/\text{FiO}_2$  ratio determination.c,d

- ii. Bilateral opacities not fully explained by effusions, lobar/lung collapse, or nodules
- iii. Respiratory failure not fully explained by cardiac failure or fluid overload; need objective assessment (e.g., echocardiography) to exclude hydrostatic edema if no risk factor present (Appendix L)

a. If altitude  $>1000\text{m}$ , then  $\text{PaO}_2/\text{FiO}_2 < 150 \times (PB/760)$ .

b. These inclusion criteria ensure a non-transient, established hypoxia that persists despite elevated PEEP and time. Initial, post-intubation, PEEP is typically  $< 8 \text{ cm H}_2\text{O}$ .

c. The qualifying  $\text{PaO}_2/\text{FiO}_2$  or the  $\text{SpO}_2/\text{FiO}_2$  must be from intubated patients receiving at least 8 cm H2O PEEP.

d. When hypoxia is documented using pulse oximetry, a confirmatory  $\text{SpO}_2/\text{FiO}_2$  ratio is required to further establish persistent hypoxia. Qualifying  $\text{SpO}_2/\text{FiO}_2$  must use  $\text{SpO}_2$  values less than or equal to 96%. Qualifying  $\text{SpO}_2$  must be measured at least 10 minutes after any change to  $\text{FiO}_2$ .

The 48-hour enrollment time window begins when criteria i-iii are met. Criteria may be met at either the Network or referring hospital. The first qualifying SpO2/FiO2 (not the confirmatory SpO2/FiO2) is used to determine this time window.

### 1.3 Exclusion Criteria

1. Lack of informed consent
2. Continuous neuromuscular blockade at enrollment
3. Known pregnancy
4. Currently receiving ECMO therapy
5. Chronic respiratory failure defined as PaCO2 > 60 mm Hg in the outpatient setting
6. Home mechanical ventilation (non-invasive ventilation or via tracheotomy) except for CPAP/BIPAP used solely for sleep-disordered breathing
7. Actual body weight exceeding 1 kg per centimeter of height
8. Severe chronic liver disease defined as a Child-Pugh score of 12-15 (Appendix A2)
9. Bone marrow transplantation within the last 1 year
10. Expected duration of mechanical ventilation < 48 hours
11. Decision to withhold life-sustaining treatment; except in those patients committed to full support except cardiopulmonary resuscitation
12. Moribund patient not expected to survive 24 hours; if CPR provided, assess for moribund status  $\geq 6$  from CPR conclusion
13. Diffuse alveolar hemorrhage from vasculitis
14. Burns  $> 70\%$  total body surface
15. Unwillingness to utilize the ARDS Network 6 ml/kg IBW ventilation protocol
16. Previous hypersensitivity or anaphylactic reaction to cisatracurium
17. Neuromuscular conditions that may potentiate neuromuscular blockade and/or impair spontaneous ventilation (Appendix A2)
18. Neurologic conditions undergoing treatment for intracranial hypertension
19. Enrollment in an interventional ARDS trial with direct impact on neuromuscular blockade and PEEP
20. PaO2/FiO2 (if available)  $>200$  after meeting inclusion criteria and before randomization *Oxygenation may improve during the 48 hour enrollment window. This exclusion criterion ensures that patients with mild ARDS are not included in the study.*
21. Endotracheal ventilation for greater than 120 hours (5 days)
22. Patient has completed lung transplant evaluation and has been officially listed for lung transplant by UNOS

### 1.4 Randomization and Study Initiation Time Window

All patients must be enrolled and randomized within 48 hours of meeting inclusion criteria. After randomization, the low tidal volume protocol must be initiated within two hours (if not already being used). In the intervention arm, deep sedation followed by neuromuscular blockade must be initiated within four hours of randomization.

## 1.5 Efficacy

The primary outcome is all-cause mortality prior to discharge home before day 90.

### 1. Secondary Outcomes:

- ICU Acquired Weakness
- IL-6 levels (plasma)
- Hospital mortality to day 28
- Ventilator free days to day 28
- Organ failure free days to day 28
- ICU-free days at day 28
- Hospital-free days at day 28
- Physiologic measures
- Long term outcome assessments
- Use of rescue procedures
- Paralysis recall, in-hospital
- Supraventricular tachycardia and new onset atrial fibrillation

## 1.6 Sample Size/Interim Monitoring

1. With a 35% mortality rate in the control arm and 27% mortality rate in the intervention arm, the maximum required total sample size is 1408 subjects.
2. The principal analysis will be intent-to-treat, based upon randomization assignment.
3. Trial progress will be evaluated by an independent Data and Safety Monitoring Board (DSMB) to determine if the study should stop for superiority of either Active or Control therapy. There will be two interim analyses and a final analyses conducted when approximately each successive 1/3 of the patients have been enrolled.

## **2. Data Analysis Plan**

### 2.1 Study Population

There is only one study population. All analyses will be by intention to treat

### 2.2 Primary Outcome

The primary outcome is intention to treat 90 day all cause in-hospital mortality, where in-hospital includes study hospital and LTAC. Patients who are discharged home (defined as residence prior to admission) prior to day 90 will be assumed to be alive at day 90. If the study does not cross a stopping boundary all patients will be followed for 90 days and the data can be analyzed using Pearson's chi-square test. However, at each interim analysis it is necessary to take into account patients who are still in the hospital with less than 90 days of follow up. This will be accomplished using the Kaplan Meier day 90 mortality point estimates with all patients who are discharged home or still alive at day 90 censored at day 91, which is beyond the last possible day of death. The 90 mortality estimates in the two treatment groups will be compared by a Z-test using Greenwood's standard error [1].

The number of interim looks and stopping boundaries are given in the protocol. At each interim look the stopping boundaries will be updated using SAS PROC SEQTEST (SAS Institute Inc.,

Cary, NC, USA.) with the information time defined by the Cutler and Ederer effective sample size [2].

The hypothesis regarding the primary outcome is a two-sided superiority hypothesis. The overall type one error is a two sided p-value of 0.05 corrected for the group sequential design as described in the protocol.

### 2.3 Analysis Methods for: Secondary Outcomes, Descriptive Variables, Safety Outcomes, Patient Characteristics

Continuous secondary outcomes will be compared between treatment groups using a t-test. Ordinal secondary outcomes (defined as outcomes with ordinal levels such as none, mild, moderate...) will be compared between groups using the Cochran-Mantel-Haenszel ANOVA (row mean score) test. Categorical secondary outcomes will be compared between treatment groups using a Chi-square or Fisher's exact test as appropriate to the sparseness of the data. All tests will use a two sided p=0.05 significance level. There will be no correction for multiple comparison.

### 2.4 On Study Variables

Variables that are measured daily, such as fluid balance, will be compared between treatment groups on each study day that they are measured.

### 2.5 Adverse Events

Adverse events will be analyzed using weighted Poisson regression with non-serious events weighted by one and serious events weighted by two. Events rather than patients will be the unit of analysis. Adverse events will be grouped and analyzed separately by MeDRA system organ classes, and MedDRA preferred term.

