# 11 ADVERSE EVENTS

## 11.1 SAFETY MONITORING

Assuring patient safety is an essential component of this protocol. Each participating investigator has primary responsibility for the safety of the individual participants under his or her care. The Investigators will determine daily if any adverse events occur during the period from enrollment through **study day 7** (five days after infusion of study drug) or ICU discharge, whichever occurs first.

The following adverse events will be collected in the adverse event case report forms:

- Serious adverse events
- Nonserious adverse events that are considered by the investigator to be related to study drug or study procedures or of uncertain relationship (Appendix C2)
- Adverse events that lead to permanent discontinuation of the study drug infusion
- Hypersensitivity reactions to cisatracurium, severe prolonged bradycardia (heart rate < 50 for > 30 minutes), and paralysis recall
- Hypotension or pneumothorax, considered by the investigator to be related to high PEEP, or of uncertain relationship.

A clinical trial adverse event is any untoward medical event associated with the use of a drug or study procedure in humans, whether or not it is considered related to a drug or study procedure.

After randomization, adverse events related to protocol procedures or occurring after the patient receives the first dose of study drug must be evaluated by the investigator. If the adverse event is judged to be reportable, as outlined above, then the investigator will report to the CCC their assessment of the potential relatedness of each adverse event to protocol procedure or study drug via electronic data entry. Investigators will assess if there is a reasonable possibility that the study drug or procedure caused the event, based on the criteria outlined in Appendix C2. Investigators will also consider if the event is unanticipated or unexplained given the patient's clinical course, previous medical conditions, and concomitant medications.

If a patient's treatment is discontinued as a result of an adverse event, study site personnel must report the circumstances and data leading to discontinuation of treatment in the adverse event case report forms.

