Serious adverse events will be collected during the first **7 study days** or until ICU discharge, whichever occurs first, regardless of the investigator's opinion of causation. Thereafter, serious adverse events are not required to be reported unless the investigator feels the events were related to either study drug or a protocol procedure.

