## **C3. CLINICAL OUTCOMES THAT MAY BE EXEMPT FROM ADVERSE EVENT REPORTING**

[figure not shown]
Study-specific clinical outcomes of ARDS, as outlined in Sections 3.8.1 and 3.8.2 (Primary and Secondary Outcomes) and Section 6.3 (Assessments During the Study) are exempt from adverse event reporting unless the investigator deems the event to be related to the administration of study drug or the conduct of study procedures (or of uncertain relationship). The following are examples of events that will be considered study specific clinical outcomes

- Death not related to the study drug or procedures.
- Cardiovascular events: need for vasoactive drugs or fluids for hypotension or hypotension.
- Respiratory events: decreased PaO2/FiO2, hypoxia, worsening acute respiratory distress syndrome, or respiratory failure.
- Hepatic events: hepatic injury or liver dysfunction that leads to an increase from baseline in the serum level of bilirubin.
- Renal events: renal failure, renal insufficiency, or renal injury that leads to an increase from baseline in serum creatinine.
- Hematologic/coagulation events: coagulopathy, disseminated intravascular coagulation, thrombocytopenia, or thrombocytosis.

Note: Arrhythmias such as heart block, ventricular tachycardia or ventricular fibrillation are not considered study specific clinical outcomes and should be recorded as adverse events if they are serious events, are considered by the investigator to be related to study drug, or lead to discontinuation of the study drug infusion.

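### SAP 2.5 double-weights serious adverse events and counts events as independent without specifying a robust variance, so a standard fit gives standard errors that are too small

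*SAP*

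**What the plan says.** SAP 2.5 is three sentences long. The model: "Adverse events will be analyzed using weighted Poisson regression with non-serious events weighted by one and serious events weighted by two". The unit: "Events rather than patients will be the unit of analysis". The breakdown: "Adverse events will be grouped and analyzed separately by MeDRA system organ classes, and MedDRA preferred term". The section gives no variance estimator, no rescaling of the weights, no form of test (Wald, score or likelihood ratio) and no significance level of its own. The level comes from SAP 2.3, whose heading includes safety outcomes: "All tests will use a two sided p=0.05 significance level". The same section rules out any multiplicity adjustment.

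Three protocol rules bear on the share of recorded events that are serious:

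- Section 11.1 limits most non-serious reporting to "Nonserious adverse events that are considered by the investigator to be related to study drug or study procedures or of uncertain relationship".
- Section 11.2 collects serious events over the first 7 study days "or until ICU discharge, whichever occurs first, regardless of the" investigator's view of cause. After that: "Thereafter, serious adverse events are not required to be reported unless the investigator feels the events were related to either study drug" or to a study procedure.
- Appendix C3 says that the expected clinical outcomes of ARDS "are exempt from adverse event reporting unless the investigator deems the event to be related to the administration of study drug" or to study procedures, or is unsure.

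The first two rules raise the serious share and the third lowers it. Neither document gives an expected value.

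**The concern.** A weight of two can be a reasonable way to make serious events count for more in a summary of harm. The difficulty is the error bar. A Poisson model takes the variance of a total to be equal to the total. That holds for a count, but not for a count in which some events have been doubled. A standard fit therefore behaves as if each serious event had been seen twice, independently.

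Taking events as the unit adds a second error in the same direction. Several events in one critically ill patient are treated as if they came from different patients.

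At stake is how the adverse-event tables can be read. Safety is part of the primary objective (Protocol 3.8), and Protocol 3.6 criticises earlier trials for weak safety reporting. Intervals that are too narrow, repeated over many organ classes and terms without adjustment, will flag spurious differences in either direction.

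**Working it through.** **Inputs.** Weights 1 and 2 and the event as unit (SAP 2.5); two-sided 5% level (SAP 2.3); 704 patients per arm (1408/2). The serious share *f*, the event rate *r* per patient and the between-patient frailty variance *v* are not in the documents. They are assumptions, shown over ranges. The plan states no error rate for this analysis, so there is no figure of its own to reproduce.

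**Weighting error.** In one arm let N be the non-serious and S the serious events, independent and Poisson. The weighted total is W = N + 2S.

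- True variance: N + 4S, proportional to 1 + 3f.
- Variance assumed by the model with raw weights: N + 2S, proportional to 1 + f.
- Ratio of true to assumed variance: (1 + 3f)/(1 + f).
- Size of the nominal 5% test: 2 × [1 − Φ(1.96/√ratio)].

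If the weights are rescaled to sum to the number of events, the ratio becomes (1 + 3f)/(1 + f)², with its maximum of 1.125 at f = 1/3 (size 6.5%).

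| Serious share f | √ratio, raw weights | Size, raw weights | Size, rescaled weights |
|---|---|---|---|
| 2% | 1.019 | 5.5% | 5.2% |
| 5% | 1.047 | 6.1% | 5.5% |
| 10% | 1.087 | 7.1% | 5.9% |
| 25% | 1.183 | 9.8% | 6.4% |
| 50% | 1.291 | 12.9% | 6.3% |
| 100% | 1.414 | 16.6% | 5.0% |

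With raw weights, nominal 95% intervals cover 94.5%, 92.9%, 90.2% and 87.1% at f = 2%, 10%, 25% and 50%.

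**Does software do this?** Take illustrative counts of 90 and 110 non-serious and 40 and 55 serious events, so the weighted totals are 170 and 220. A weighted Poisson fit, with the weights entered as frequency or as variance weights, returns a standard error of 0.102 = √(1/170 + 1/220). The correct value for independent events is √(250/170² + 330/220²) = 0.124.

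**Clustering.** With gamma frailty, the raw-weight ratio becomes (1 + 3f)/(1 + f) + r·v·(1 + f). For rescaled weights, divide this by (1 + f).

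| f | Raw: r=0.1, v=1 | Raw: r=0.3, v=3 | Rescaled: r=0.1, v=1 | Rescaled: r=0.3, v=3 |
|---|---|---|---|---|
| 5% | 7.4% | 17.0% | 6.7% | 16.0% |
| 10% | 8.5% | 18.4% | 7.1% | 16.3% |
| 25% | 11.3% | 21.7% | 7.6% | 16.8% |
| 50% | 14.6% | 25.9% | 7.5% | 16.7% |

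Patient-level simulation (704 per arm, 10,000 replicates) agrees with the formulas to within 0.6 percentage points.

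**Small counts** (raw weights, independent events, 400,000 replicates).

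| f | Wald, 20 per arm | Wald, 10 per arm | Wald, 2 per arm | Likelihood ratio, 2 per arm |
|---|---|---|---|---|
| 2% | 5.0% | 4.6% | 0.1% | 10.1% |
| 5% | 5.6% | 5.2% | 0.1% | 10.9% |
| 10% | 6.6% | 6.2% | 0.2% | 12.1% |
| 25% | 9.2% | 8.8% | 0.7% | 15.4% |
| 50% | 12.5% | 12.0% | 1.6% | 19.8% |
| 100% | 16.6% | 16.3% | 3.2% | 24.8% |

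At 2 expected events per arm, the Wald test is undefined whenever an arm has no event: 1 − (1 − e⁻²)² = 25% of datasets.

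**Check of the remedy.** One weighted total per patient, with a patient-level sandwich variance and no offset, has size 4.6% to 5.5% in all 24 non-sparse settings simulated (six values of f, four pairs of r and v). A permutation test of the per-patient totals has size 0.5–0.7%, 2.0–3.0% and 2.7–3.8% at 2, 5 and 10 events per arm.

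**The case against.** The strongest reply is that SAP 2.5 is silent on the variance and does not exclude a robust one. Raw weights and a model-based standard error are a reading of the text, and rescaled weights would bring the weighting error down to 6.5% at most. That is correct, and the size figures are conditional on that reading. But a plan exists to fix such choices in advance, and the stated rule, put into standard software, gives the faulty standard error. Rescaling also does nothing for clustering.

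The serious share is assumed, and 12.9% belongs to the upper end of the 2% to 50% range. This stands, which is why the range is shown.

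Many preferred terms will be sparse, where the ample-count figures do not apply and even the direction of the error depends on the unstated test. This also stands. The larger clustering figures likewise suit pooled tables or common organ classes: at 10 events per arm (r = 10/704 = 0.014), v = 3 moves the raw-weight size at f = 25% only from 9.8% to 10.4%.

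Finally, no stated decision rests on these p-values. The notification rule in Protocol Appendix C depends on a DSMB determination, and the safety outcomes listed in SAP Appendices A1 and A2 have patient-level tests of their own. That limits the consequence but does not make the intervals right.

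**Conclusion.** The concern holds. Fitted in the standard way, the rule in SAP 2.5 understates the variance of the treatment comparison for adverse events. With raw weights, model-based standard errors, independent events and ample counts, the nominal 5% test has a size of 5.5% to 12.9% at assumed serious shares of 2% to 50%, and 16.6% if every event in a group is serious. Clustering within patients makes it worse, by an amount the documents do not allow one to fix. For sparse terms the test may be conservative, undefined or anti-conservative, depending on a choice the SAP does not make.

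The effect is modest and limited to the adverse-event tables. The primary outcome, the stopping boundaries, the efficacy secondaries, the Appendix A1 and A2 safety tests and the Appendix C notification rule are not affected. It should be corrected because the remedy is simple and the present wording leads to intervals that do not have their stated coverage.

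**What to change.** Keep the severity weights if they are wanted, and amend SAP 2.5 to say that:

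- each randomised patient contributes one weighted total per organ class or term (zero if there was no event), compared between arms by Poisson regression with a patient-level robust (sandwich) variance and no days-at-risk offset;
- sparse terms, for example those with fewer than about 10 events per arm, are compared by a permutation test of the per-patient weighted total;
- the proportion of patients with at least one serious adverse event is reported alongside.

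The Appendix C notification rule and the Appendix A1 and A2 tests stay as they are.

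The cost is two or three sentences and a few lines of code, with no new data. There are three downsides. Intervals will be wider. The permutation test is conservative and has little power for rare terms: six affected patients, all in one arm, give p = 2 × (1/2)⁶ = 0.031, while five give 0.063, so fewer than six can never reach 0.05. And without an offset, the totals will also reflect any difference between arms in ICU stay within the 7-day collection window, which should be noted when the tables are read. The cut-off of about 10 events is a matter of judgement; what matters is that it is fixed in advance.

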## 9.1 RISKS OF NEUROMUSCULAR BLOCKADE

Potential risks of cisatracurium are bradycardia (developed in 1 of 340 patients in ACURASYS; 0.4% incidence per FDA package insert), hypersensitivity reaction (~0.2%) and ICU acquired weakness. The true risk and relationship between neuromuscular blockade and paresis is unclear and have been recently challenged. An increased risk for the development of ICU acquired weakness was not observed in patients randomized to neuromuscular blockade in the ACURASYS trial. The accompanying deep sedation that is always given with neuromuscular blockade may result in hypotension requiring vasopressor support and/or a longer total period of sedation. The neuromuscular blockade and the accompanying deep sedation may decrease risk of pain or discomfort, but may also render detection of pain or discomfort more difficult.

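### SAP 2.5 applies weighted Poisson regression to every MedDRA term without naming a test statistic or a rule for small or zero counts, so results for rare terms depend on the software's choice of test

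*SAP*

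**What the plan says.** SAP 2.5 gives one method for adverse events: "Adverse events will be analyzed using weighted Poisson regression with non-serious events weighted by one and serious events weighted by two". It adds: "Events rather than patients will be the unit of analysis". The level of analysis follows: "Adverse events will be grouped and analyzed separately by MeDRA system organ classes, and MedDRA preferred term". The section does not say whether the p-value comes from a Wald, likelihood-ratio or score test, sets no minimum count, and offers no alternative when one arm has no events. It also does not define how the weights enter the model.

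SAP 2.3 does deal with sparse data: "Categorical secondary outcomes will be compared between treatment groups using a Chi-square or Fisher's exact test as appropriate to the sparseness of the data". Its heading mentions safety outcomes, but that sentence is about secondary outcomes, and 2.5 sets a different method for adverse events. SAP 2.3 also supplies the threshold used below: "All tests will use a two sided p=0.05 significance level". It makes no multiplicity correction.

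SAP Appendix A1 assigns Fisher's exact test to paralysis recall, supraventricular tachycardia or new atrial fibrillation, pneumothorax and rescue procedures. Hypersensitivity and bradycardia are not in that table. Protocol 11.1 collects hypersensitivity to cisatracurium and severe prolonged bradycardia as adverse events, and Protocol 9.1 gives incidences of about 0.2% for hypersensitivity and 0.4% for bradycardia (with 1 bradycardia case in 340 patients in the earlier trial).

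**The concern.** Preferred terms are the finest level of adverse-event coding, and many will have only a handful of events. A reaction caused by the drug may also have none in controls. Poisson regression relies on large-sample approximations that fail there. With a zero cell the rate ratio has no finite estimate, and the usual p-values from the same model can disagree completely.

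Safety is part of the trial's primary objective (Protocol 3.8). If the statistic is not fixed in advance, a software default could decide whether a rare term is reported as a clear difference or as no difference at all.

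**Working it through.** **Inputs.** Maximum sample size 1408 (Protocol section 7). The allocation ratio is not stated; 1:1 is assumed, giving 704 per arm. Two-sided 0.05 is from SAP 2.3. Event rates are from Protocol 9.1. Events are taken as independent with equal exposure in each arm.

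**Arm size.** For 35% v 27%, two-sided 0.05 and power 0.90: n per arm = [1.960 × √(2 × 0.31 × 0.69) + 1.282 × √(0.35 × 0.65 + 0.27 × 0.73)]² / 0.08² = 700.3, so 701 per arm and 1402 in total. The plan's 1408, which also carries the sequential design, is consistent with this.

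**Expected events in 704 treated patients.** Hypersensitivity: 704 × 0.002 = 1.4. Bradycardia: 704 × 0.004 = 2.8, or 704 / 340 = 2.1 at the earlier trial's rate. A near-zero control rate is an assumption.

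**p-values for k events v 0, weight 1**
- Wald: the log rate ratio is infinite. A fitted model at 6 v 0 returned an estimate of 22.4 with standard error 17985, p = 0.999.
- Likelihood ratio: χ² = 2k ln 2 on 1 df.
- Score: χ² = (k − 0)² / k = k on 1 df.
- Exact conditional: p = 2 × (1/2)^k.

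| Events | Wald | Likelihood ratio | Score | Exact | Fisher, 704 v 704 |
|---|---|---|---|---|---|
| 2 v 0 | ~1 | 0.096 | 0.157 | 0.50 | 0.50 |
| 3 v 0 | ~1 | 0.041 | 0.083 | 0.25 | 0.25 |
| 4 v 0 | ~1 | 0.019 | 0.046 | 0.125 | 0.125 |
| 6 v 0 | ~1 | 0.004 | 0.014 | 0.031 | 0.031 |
| 8 v 0 | ~1 | 0.001 | 0.005 | 0.008 | 0.008 |

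The first one-sided count to reach 0.05 is 3 v 0 by likelihood ratio, 4 v 0 by score and 6 v 0 by either exact test. Wald never reaches it.

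**Serious events.** If the weight of two acts as a doubled count, 2 v 0 is analysed as 4 v 0: likelihood ratio p = 0.0185 and score p = 0.0455, against an exact p of 0.50.

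**False-positive rate, weight 1.** With the same Poisson mean m in both arms, sum Poisson(x; m) × Poisson(y; m) over all pairs (x, y) with p < 0.05.

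| m per arm | Likelihood ratio | Score | Exact |
|---|---|---|---|
| 0.5 | 1.8% | 0.2% | <0.1% |
| 0.8 | 4.3% | 0.8% | <0.1% |
| 1 | 6.0% | 1.4% | <0.1% |
| 1.5 | 8.8% | 3.0% | 0.2% |
| 2 | 9.7% | 4.1% | 0.5% |
| 3 | 8.8% | 4.7% | 1.2% |
| 5 | 7.1% | 4.4% | 2.2% |
| 10 | 5.4% | 5.2% | 2.9% |

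**Power of the exact conditional test at the protocol's rates.** With 0.1 expected control events it is 0.3% at 1.4 events on drug and 6% at 2.8. At 2.8 v 0.1 the score test has 28%.

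**The case against.** The strongest reply is that the SAP names no statistic, so no particular failure is planned. A score test would be a legitimate choice, and for non-serious events it stays close to or below 5% throughout the table. That stands. A reader might infer that one-arm-only events will necessarily get either p near 1 or significance at 3 v 0; the documents do not support that either/or. The score test is less reassuring for serious events, where a doubled count makes it reject at 2 v 0.

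Nor do the documents support a wider reading that cisatracurium's safety signals in general rest on this method. Appendix A1 gives Fisher's test to several rare outcomes, including paralysis recall. Serious study-related events also go to the coordinating center within 24 hours, with Medical Monitor assessment and DSMB review (Protocol 11.2, Appendices C and H). A preferred-term p-value is not the only route of detection.

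Three further limits stand. The likelihood-ratio excess is a peak, not a general rate: below about 0.8 expected events per arm the test is conservative. Zero control events is an assumption, since controls may receive open-label cisatracurium (Protocol 5.2.1), and the 0.4% is the package-insert figure for bradycardia, whereas the trial collects a severe, prolonged form. Finally, a reader might infer that an exact test would find these two events; at the protocol's rates it almost never would.

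**Conclusion.** The point holds as a gap in a stated method. SAP 2.5 sends every term, however rare, through one weighted regression, and the result at low counts depends on an unstated statistic. At 6 v 0 non-serious events the p-value ranges from 0.004 to about 1, against an exact 0.031. The likelihood-ratio test can declare a difference at 3 v 0, where the exact p is 0.25. For serious events the threshold falls to 2 v 0 (exact 0.50), provided the weight acts as a doubled count.

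This matters chiefly for hypersensitivity, bradycardia and other rare terms outside Appendix A1. It rests on 704 per arm, independent events and, for the one-arm-only pattern, a near-zero control rate. It concerns safety reporting and leaves the primary analysis untouched. The change should be made because it is cheap and the SAP already applies the same principle to other sparse outcomes.

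**What to change.** Amend SAP 2.5 as follows.
- Set an event count in advance (for example, fewer than 10 in either arm; the exact figure is a matter of choice). Below it, for any preferred term or organ class, replace the weighted regression with an unweighted exact comparison: Fisher's test on patients with at least one event, or an exact conditional test on events.
- Report counts by arm with an exact interval, and show serious events separately.
- Keep the regression for larger groupings, where the SAP's choice of events as the unit can stand, and name its test statistic.

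The interval does most of the work. For k v 0 events with equal exposure, the lower 95% limit for the share of events in the active arm is s = 0.025^(1/k), and for the rate ratio s / (1 − s). At 3 v 0 this is 0.292 / 0.708 = 0.41; at 6 v 0 it is 0.541 / 0.459 = 1.18. The upper limit is unbounded in both cases.

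The cost is a few sentences and a few lines of code, with no new data. Exact tests are conservative and have little power at the protocol's rates, so a non-significant result must not be read as absence of harm. Patient-level Fisher also ignores repeat events, which can be listed.
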